### **2.8.2 Deaths**

Separate summaries for on-treatment and all deaths (on-treatment and post-treatment) will be produced by treatment arm, system organ class and preferred term. All deaths will be listed, post treatment deaths will be flagged.

### **2.8.3 Laboratory data**

Laboratory, data summaries will include all assessments available for the lab parameter collected no later than 30 days after the last study treatment administration date, using data from all sources (central and local laboratories). All laboratory assessments will be listed and those collected later than 30 days after the last study treatment date will be flagged in the listings.

Grade categorization of lab values will be assigned programmatically as per NCI Common Terminology Criteria for Adverse Events (CTCAE) version 4.03. The calculation of CTCAE grades will be based on the observed laboratory values only, clinical assessments will not be taken into account. The criteria to assign CTCAE grades are given in <Novartis internal criteria for CTCAE grading of laboratory parameters>. The latest available version of the document based on the underlying CTCAE version 4.03 at the time of analysis will be used. The Novartis internal CTCAE grading document will be added as appendix to the CSR.

For laboratory tests where grades are not defined by CTCAE v4.03, results will be graded by the low/normal/high (or other project-specific ranges, if more suitable) classifications based on laboratory normal ranges.

A severity grade of 0 will be assigned for all non-missing lab values not graded as 1 or higher. Grade 5 will not be used. For laboratory tests that are graded for both low and high values,

summaries will be done separately and labelled by direction, e.g., sodium will be summarized as hyponatremia and hypernatremia.

In rare cases where multiple lab measurements meet the baseline definition, with no further flag or label that can identify the chronological order then the following rule should be applied: If values are from central and local laboratories, the value from central assessment should be considered as baseline. If multiple values are from the same laboratory (local or central) then the value with the last sequence/repeat number should be considered as baseline.

A listing of laboratory values will be provided by laboratory test, patient, and study day. A separate listing will display notable laboratory abnormalities (i.e., newly occurring CTCAE grade 3 or 4 laboratory abnormalities).

The following by-treatment summaries will be generated separately for hematology and biochemistry laboratory tests:

- shift tables using CTCAE grades to compare baseline to the worst on-treatment value
- for laboratory tests where CTCAE grades are not defined, shift tables using the low/normal/high/(low and high)
- listing of all laboratory data with values flagged to show the corresponding CTCAE grades and the classifications relative to the laboratory normal ranges.
- Boxplots of hematological parameters (hemoglobin and platelet count) over time

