**Document History – Changes compared to previous final version of SAP**

Date	Time point	Reason for update	Outcome for update	Section and title impacted (Current)
29-Jan-2016	Prior to DB lock	Creation of final version	N/A - First version	NA
19-Jul-2017	Prior to DB lock	Creation of amendment 1 due to study premature termination	Change to the ultimate goal of the early termination study: To present the efficacy, safety and [REDACTED] data of interest.	Introduction section 1.2
			Specified that primary endpoint PFS, and other time to event endpoints will not be derived.	Introduction section 1.2
			Removed Per-Protocol Set and PK Set, and Subgroup of interest.	Analysis sets Section 2.2
			Treatment period 1 data will be tabulated, Treatment period 1 and period 2 data will be listed.	Sections 2.3, 2.4, 2.5, 2.7, 2.8
			Specified that no analysis for primary endpoint is planned. The early terminated study aims to present data collected for the endpoints of interest, including change in spleen volume and length from baseline, change in symptoms using MF-7 and EQ-5D from baseline (see patient reported outcomes section), safety endpoints, [REDACTED]	Analysis of the primary objective section 2.5
			Descriptive statistics will be used to summarize the endpoints of interest and the FAS will be used for analyzing the data.	
			Specified that no sufficient data were collected to assess the effect of ruxolitinib versus placebo on overall survival and time to progression, so that no secondary	Analysis of the secondary objectives section 2.7

Date	Time point	Reason for update	Outcome for update	Section and title impacted (Current)
			efficacy analysis will be performed in this study.	
			AESI is not planned for this prematurely terminated study.	Section 2.8.1.1
			Add text to AE of clinical trial safety disclosure.	Section 2.8.1.2
			No formal PK analysis is planned. Individual plasma ruxolitinib concentration data will only be listed for the Full analysis set.	PK Section 2.9
				

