### 2.1.6 Last date of study treatment

The last date of study treatment is defined as (1) the date of last administration of study treatment in treatment period 1 if the patient never went to treatment period 2 or (2) the date of last administration of study treatment in treatment period 2 if the patient went to treatment period 2.

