## 2.8 Safety analyses

For all safety analyses, the safety set will be used. All listings and tables will be presented by treatment group.

The overall observation period will be divided into four mutually exclusive segments:

**pre-treatment period:** from day of patient's informed consent (molecular pre-screen or main study informed consent) to the day before the first administration of study treatment

**on-treatment period 1:** from day of start of study treatment to minimum of (1) 30 days following the last date of study treatment in period 1 and (2) start of open label ruxolitinib in treatment period 2:

[Start date of study treatment; min(last date of study treatment in treatment period 1 + 30 days, start date of open label ruxolitinib in treatment period 2 – 1 day)].

**on-treatment period 2:** from start day of open label ruxolitinib to 30 days following the last date of study treatment in period 2:

[Start date of open label ruxolitinib in treatment period 2; last date of open label ruxolitinib in treatment period 2 + 30 days].

**post-treatment period:** starting at day 31 after last dose of study treatment.

On-treatment assessment is defined as any assessment reported in the on-treatment period 1 or 2.

Safety summaries (tables, figures) include data from the pre-treatment period (to display the baseline status) and the on-treatment period 1. Data from the on-treatment period 2 (if provided) and the post-treatment period (if provided) with the exception of deaths should not be included.

In particular, summary tables for adverse events (AEs) will summarize only on-treatment events, with a start date during the on-treatment period 1, the so-called *treatment-emergent* AEs for period 1.

However, all safety data (including those from the post-treatment period if provided) will be listed and those collected during the pre-treatment, treatment period 2 and post-treatment period will be flagged.

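### The laboratory-summary window in SAP 2.8.3 runs into open-label Treatment Period 2, although SAP 2.8 limits safety tables and figures to on-treatment period 1

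*SAP*

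**What the plan says.** SAP 2.8 gives the rule for all safety output: "Safety summaries (tables, figures) include data from the pre-treatment period (to display the baseline status) and the on-treatment period 1". It then names the exclusion: "Data from the on-treatment period 2 (if provided) and the post-treatment period (if provided) with the exception of deaths should not be included". On-treatment period 1 ends at the "minimum of (1) 30 days following the last date of study treatment in period 1 and (2) start of open label ruxolitinib", and the bracketed formula in that section takes the second limit as the day before the first open-label dose. For adverse events the section repeats the restriction: "summary tables for adverse events (AEs) will summarize only on-treatment events, with a start date during the on-treatment period 1". The SAP's document history states the same intent: "Treatment period 1 data will be tabulated, Treatment period 1 and period 2 data will be listed".

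SAP 2.8.3 has its own inclusion sentence. Laboratory summaries take in "all assessments available for the lab parameter collected no later than 30 days after the last study treatment administration date", from central and local laboratories. It does not mention period 1 and has no cut at the start of open-label treatment. The outputs listed there include shift tables from baseline to the worst value on treatment, and boxplots of hemoglobin and platelets over time.

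Three definitions bear on how that sentence is programmed:

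- SAP 2.1.6 sets the last date of study treatment as "the date of last administration of study treatment in treatment period 2 if the patient went to treatment period 2". SAP 2.1.3 separately defines the last dose in period 1.
- SAP 2.8 states: "On-treatment assessment is defined as any assessment reported in the on-treatment period 1 or 2".
- SAP 2.2.2 analyses a patient under the randomized treatment once at least one dose of it has been taken.

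**The concern.** A programmer who follows 2.8.3 and one who follows 2.8 will produce different laboratory tables from the same SAP. Under 2.8.3, a placebo patient who progressed and moved to open-label ruxolitinib would have ruxolitinib blood counts tabulated in the placebo column. A ruxolitinib patient would have values from the blinded 10 mg BID schedule mixed with values from the period 2 schedule of 5, 15 or 20 mg BID (Protocol 6.1.1). Protocol 1.2.1.2.3 describes anemia, thrombocytopenia and neutropenia as dose related, so the hematology tables are the ones most exposed. The laboratory tables would also cover a different period from the adverse event tables, which are held to period 1.

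**Working it through.** There is no plan figure to reproduce. The check compares the end dates of the two windows.

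**Notation.** L is the last blinded dose, the first open-label dose is at L + g, and M is the last open-label dose. The SAP gives no values for g or M, so those used below are assumptions.

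**Window ends**

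| Rule | Last day admitted | Open-label days admitted |
|---|---|---|
| SAP 2.8 | min(L + 30, L + g − 1) | 0 for every g |
| SAP 2.8.3, last dose as in 2.1.6 | M + 30 | all of period 2, plus 30 days |
| SAP 2.8.3, last dose as in 2.1.3 | L + 30 | (L + 30) − (L + g) + 1 = 31 − g, not below 0 |

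**Narrower (2.1.3) reading.** g = 1 gives 30 days, g = 7 gives 24, g = 14 gives 17, and g of 31 or more gives 0.

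**Worked case (assumed days).** Take L = 200, first open-label dose on day 201 and M = 400.

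- SAP 2.8: min(200 + 30, 201 − 1) = day 200.
- SAP 2.8.3 with 2.1.6: 400 + 30 = day 430.
- SAP 2.8.3 with 2.1.3: 200 + 30 = day 230, which admits open-label days 201 to 230.

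**Is a short gap realistic?** Protocol 7.1.4 places the End of Treatment Period 1 assessments within 2 weeks before the first open-label dose. A gap of 1 to 14 days is therefore plausible if blinded dosing continues to that visit. The minimum in SAP 2.8 would itself be unnecessary if open-label treatment could not start inside the 30 days.

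**Are there laboratory values in the extra time?** Protocol Table 7-1 B schedules hematology and chemistry throughout period 2, so the 2.1.6 reading brings in whole series of values. The narrower reading brings in few scheduled values (see the objection).

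**Effect on a shift table.** Adding later values can only leave a patient's worst grade unchanged or raise it. One entrant therefore changes the proportion at or above a given grade by at most 1/n of the arm, per parameter: 100/5 = 20, 100/10 = 10 and 100/20 = 5 percentage points at assumed arm sizes of 5, 10 and 20. Within an arm the proportion can only stay the same or rise. Patients from either arm can enter period 2, so the effect on the between-arm contrast has no fixed direction.

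**The case against.** The strongest answer is that 2.8 is the parent section and already governs. It opens by covering all safety analyses, names deaths as the only exception, and is backed by the document history. On this view the 2.8.3 sentence only sets a latest date and the data sources, and applying both rules together leaves baseline plus period 1. The intent is indeed clear. But 2.8.3 is worded as an inclusion rule for all assessments, is the more specific text, and is not corrected elsewhere in its section. The worst-value shift tables rely on a definition of on-treatment that includes period 2. The parent rule shows which text should give way, but it does not make the two agree.

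Two limits on size stand.

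- The wording in 2.8.3 matches neither 2.1.6 nor 2.1.3 exactly, so admission of all of period 2 is one reading and not a certainty.
- On the narrower reading, counting days overstates the data involved. Table 7-1 B has no hematology at the first open-label dose, and the first is at Week 4 (Day 28). If Day 1 is the first open-label dose, that visit falls at L + g + 27. It is inside L + 30 only for g of 3 or less, or 6 or less using the 3-day allowance. If the period 1 schedule simply continues, as Protocol 7.1.4 indicates, visits are 4, 8 or 12 weeks apart. The extra days then usually hold one scheduled visit or none. Unscheduled values could add to this.

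The vital-signs text in SAP 2.8.4.2 has no competing window. It shares the broad on-treatment definition, which is an ambiguity and not a contradiction.

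**Conclusion.** The concern holds, as a minor point. SAP 2.8.3 as written admits open-label values that SAP 2.8 excludes. This is so for every period 2 entrant on the 2.1.6 reading, and on the 2.1.3 reading whenever open-label treatment starts within 30 days of the last blinded dose. The Safety Set rule then places those values under the randomized arm, including placebo.

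The practical size is unknown. The number of period 2 entrants is not given, SAP 1.2 describes both the number randomized and the study duration as minimal, and with no entrants the effect is zero. The bound of 100/n points per entrant and parameter rests on assumed arm sizes, and the day counts rest on an assumed gap. No hypothesis test is affected, because the SAP is descriptive throughout. Confidence is high that the two sections do not agree, and lower on how much data the wider window would bring in.

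**What to change.** In SAP 2.8.3, replace the 30-day limit in the inclusion sentence with a reference to the pre-treatment period (for baseline) and on-treatment period 1 as defined in 2.8. Add a period 1 qualifier to the worst-value shift tables and, for clarity, to the vital-sign summaries in 2.8.4.2. Period 2 values stay in the listings and are flagged, as 2.8 already requires, so no data are lost.

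The cost is one clause, one qualifier used in two places, and one date filter in the programs.

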#### **2.8.4 Other safety data**

Analyses will be performed on the safety set.

##### **2.8.4.1 ECG and cardiac imaging data**

A standard 12 lead ECG will be performed at screening, every 48 weeks and at the end of

Treatment, read and interpreted locally per protocol specifications. The ECG data will be listed.

##### **2.8.4.2 Vital signs**

Vital sign assessments are performed in order to characterize basic body function. The following parameters were collected: height (cm), weight (kg), body temperature (°C), heart rate (beats per minute), systolic and diastolic blood pressure (mmHg), and respiratory rate (per minute).

#### **Data handling**

Vital signs collected during on-treatment will be summarized. Values measured outside of on-treatment period will be flagged in the listings.

#### **Data analysis**

For analysis of vital signs the notable criteria are provided in Table 7-1 below.

**Table 2-3 Notable Criteria for vital signs**

Vital sign (unit)	Notable high value	Notable low value
Weight (kg)	increase $\geq$ 10% from baseline	decrease $\geq$ 10% from baseline
Systolic blood pressure (mmHg)	$\geq$ 180 and increase from baseline of $\geq$ 20	$\leq$ 90 and decrease from baseline of $\geq$ 20
Diastolic blood pressure (mmHg)	$\geq$ 105 and increase from baseline of $\geq$ 15	$\leq$ 50 and decrease from baseline of $\geq$ 15
Pulse rate (bpm)	$\geq$ 100 and increase from baseline of $>$ 25%	$\leq$ 50 and decrease from baseline of $>$ 25%
Body temperature ( $^{\circ}$ C)	$\geq$ 39.1	--

Summary table will be produced for vital signs. The table will include descriptive statistics at baseline, one or several post-baseline time points and change from baseline to this/these post-baseline time points.

A listing of all vital sign assessments will be produced by treatment arm and notable values will be flagged. In the listing, the assessments collected outside of on-treatment period will be flagged as well as assessments made in treatment period 2.

## 2.9 Pharmacokinetic endpoints

All individual plasma ruxolitinib concentration data will be listed for the Full analysis set.

### Handling of PK data below LLOQ or missing

All concentration values below the lower limit of quantitation (LLOQ) (0.50 ng/mL) are set to zero by the Bioanalyst, and will be displayed in the listings as zero and flagged. Missing values for any PK data will not be imputed and will be treated as missing.

## 2.11 Patient-reported outcomes

There are several patient reported outcomes measured in the study, including the Myeloproliferative Neoplasm-Symptom Assessment Form (MF-7) Total Symptom Score, the EQ-5D and [REDACTED]. The FAS will be used for analyzing PRO data. No formal statistical test will be performed.

### Change in symptoms using MF-7

The MF-7 total symptom score is among the key patient reported outcome variables of interest. It will be used to collect data on the impact of ruxolitinib treatment on the patient's disease-related symptoms, functioning and overall quality of life. No formal statistical test

will be performed. Percent change from Baseline in MF-7 total symptom score and 7 individual symptoms at each visit will be summarized with descriptive statistics.

Missing items data in a PRO scale will be handled based on each instrument manual. All PRO analyses will include data as imputed according to the scoring manual. No imputation will be applied if the total or subscale scores are missing at a visit.

[figure not shown]
[figure not shown]

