5.2 Inclusion criteria

Patients eligible for inclusion in this study have to meet **all** of the following criteria at screening:

Written informed consent must be obtained prior to any screening procedures.

1. Male or Female aged 18 or over.
2. Confirmed diagnosis of MF with bone marrow fibrosis of at least Grade 1 ([Appendix 2](#)); irrespective of JAK2 mutational status.

3. Patients with at least one mutation in one of the five HMR genes (ASXL1, EZH2, SRSF2 and IDH1/2).
4. Patients with non-palpable spleen or spleen palpable ≤ 5 cm from the left costal margin to the point of greatest splenic protrusion.
5. Patients with MF-7 score of ≤ 15 , with each individual symptom score of ≤ 3 .
6. Patients with a peripheral blood blast count percentage of $< 1\%$.
7. Patients with Hemoglobin $> 10\text{g/dL}$.
8. Patients with platelet counts $\geq 75,000/\mu\text{L}$.
9. Patients with Absolute neutrophil count (ANC) $\geq 1000/\mu\text{L}$.
10. Patients with WBC $\leq 15 \times 10^3/\mu\text{L}$.
11. Patients with an Eastern Cooperative Oncology Group (ECOG) performance status of 0, 1, or 2.

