7.1.2 Screening

[figure not shown]
Patients will be consented to the main study informed consent after obtaining a central confirmation of HMR positivity. There will be a 40 day screening period (Day -40 to -Day -1). Screening procedures are outlined in the visit evaluation schedule ([Table 7-1 \[A\]](#)).

Upon completion of all routine screening procedures and all other eligibility criteria including patient history, laboratory assessments, and symptom score assessments should be performed.

A bone marrow biopsy should be performed, unless adequate archival tissue is available for the patient from a procedure performed within the last 6 months prior to randomization. Biopsy specimen and marrow aspirate must be sent to a Novartis designated laboratory for central analysis. Upon receipt of the bone marrow biopsy grade confirming patient eligibility, the investigator must perform the MRI (or CT for applicable patients) scan and send to the central imaging laboratory for assessment the same day as the scan. MRI/CT should be performed within 7 days prior to randomization.

A patient who has a laboratory test result(s) that does not satisfy the entrance criteria may have the test(s) repeated. These tests may be repeated as soon as the investigator believes the retest result is likely to be within the acceptable range to satisfy the entrance criteria, but should be completed within 40 days of the original screening visit date. In this case, the subject will not be required to sign another ICF, and the original patient ID number assigned by the investigator will be used. In the event that the laboratory test(s) cannot be performed within 40 days of the original screening visit, or the retest(s) do not meet the entrance criteria or the patient's medical condition has change significantly during the screening phase so that the inclusion/exclusion criteria are no longer met, the patient is considered a screen failure.

A new ICF will need to be signed if the investigator chooses to re-screen the patient after a patient has screen failed. The subject number will remain unchanged and patient will be entered in the IRT as re-screen. All required screening activities must be performed when the patient is rescreened for participation in the study. An individual patient may only be rescreened once for the study.

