7.1.2.3 Patient demographics and other baseline characteristics

Patients will have the following assessments performed at screening:

- Review of medical history, prior anti-neoplastic therapy related to hematologic disease, prior concomitant medications and adverse events
- Disease diagnosis confirmed by a Novartis designated laboratory ([Section 7.1.2](#)) using a bone marrow biopsy and aspirate
- Physical examination including height, weight, performance status, vital signs and measurement of spleen length by palpation ([Section 7.2.2](#))
- Laboratory assessments – Hematology, serum chemistry, coagulation, urinalysis, pregnancy test (if applicable) and hepatitis test ([Section 7.2.2](#))
- Patient reported outcomes – MF-7, EO-5D and [REDACTED] questionnaires.

- Electrocardiogram (ECG)
- MRI/CT of the spleen to determine spleen volume by central imaging laboratory

The investigator must confirm all the inclusion and exclusion criteria prior to contacting IRT for randomization of the patient. Once the patient's eligibility is confirmed, the patient must have baseline assessments performed on Day 1 prior to randomization and treatment initiation (Table 7-1).

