1. MF-7
2. EQ-5D-5L

Patient Reported Outcomes will be collected according to the Visit Schedule outlined in [Table 7-1](#). The patient should be given sufficient space and time to complete the PRO questionnaires. The site personnel should check the questionnaires for completeness and ask the patient to complete any missing responses. The original questionnaire will be kept with the patient’s file as the source document.

[figure not shown]
Completed questionnaire(s) and any unsolicited comments written by the patient should be reviewed and assessed by the investigator for responses which may indicate potential AEs or SAEs before any clinical study examinations. This assessment should be documented in study source records. If AEs or SAEs are confirmed, study investigators should not encourage the patient to change responses reported in the completed questionnaires. Study investigators must follow reporting instructions outlined in [Section 8](#) (e.g. reference “Adverse Events” section) of the study protocol.

MF-7

The Myelofibrosis 7 Item Symptom Scale (MF-7) ([Appendix 4](#)) is a disease specific questionnaire comprised of 7 items that measures the severity of seven of the most prevalent associated symptoms including: tiredness, early satiety, abdominal discomfort, night sweats, itching (pruritus), bone pain (diffuse not joint or arthritis) and pain under ribs on left side. Each item is scored on a scale ranging from 0 (absent) to 10 (worst imaginable). The MF-7 score is computed as the sum of the observed scores in the individual items to achieve a 0-to-70 score. There would be one recall period of 24 hours used in this questionnaire.

EQ-5D-5L

EQ-5D-5L ([Appendix 4](#)) is a standardized instrument for measuring health outcomes in a wide range of health conditions and treatments. It consists of a descriptive system and a visual analogue scale (EQ VAS). The descriptive system comprises the following 5 dimensions: mobility, self-care, usual activities, pain/discomfort and anxiety/depression. Each dimension has 5 levels: no problems, slight problems, moderate problems, severe problems and extreme problems. The EQ VAS records the respondent’s self-rated health on a vertical, visual analogue scale where the endpoints are labeled ‘Best imaginable health state’ and ‘worst imaginable health state’. The EQ-5D scores can be summarized into a single index score that provides a simple measure of health for clinical and economic appraisal.

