### 2.1.8 Baseline

Baseline values for safety and non-safety evaluations are defined as below unless specified otherwise in the RAP.

For *safety evaluations* (e.g. laboratory and vital signs), the last assessment available before or on the start date of study treatment in period 1 (only if such assessment are pre-dose) is taken as a “baseline” assessment.

For *efficacy and other non-safety evaluations* (e.g. MRI / CT scan), the last available assessment before or on the day of randomization is taken as the “baseline” value or “baseline” assessment. Multiple assessments on the same day are not expected.

If patients have no assessments as defined above, the baseline result will be missing.

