### 2.1.10 Windows for multiple assessments

In order to summarize data collected over time (including unscheduled visits), the assessments will be time slotted. The following general rule will be applied in creating the assessment windows: If more than one assessment is done within the same time window, the assessment performed closest to the target date will be used. If 2 assessments within a time window are equidistant from the target date, then the later of the 2 assessments will be used. Data from all assessments (scheduled and unscheduled), including multiple assessments, will be listed.

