## **2.5 Analysis of the primary objective**

The study was terminated prematurely with insufficient sample size and study duration to evaluate the effect of ruxolitinib in delaying progression of MF from early disease to more advanced disease stages. Therefore, the initial primary end point, progression free survival

(PFS), will not be derived and no statistical hypothesis will be tested. Consequently, no supportive analysis for per protocol set is planned.

The early terminated study aims to present data collected for the endpoints of interest, including change in spleen volume and length from baseline, change in symptoms using MF-7 and EQ-5D from baseline (see patient reported outcomes section), safety endpoints [REDACTED]. Descriptive statistics will be used to summarize the endpoints of interest and the FAS will be used for analyzing the data. Change in spleen volume and palpable spleen length below costal margin

Regular assessments of spleen volumes via Magnetic Resonance Imaging (MRI) or Computed Tomography (CT) are performed to evaluate progressive splenomegaly. Spleen size is assessed by palpation and measured in centimeters using a soft ruler, from the costal margin to the point of greatest splenic protrusion.

Spleen volume, spleen length, absolute change and percentage change in spleen volume by MRI/CT and palpable spleen length below costal margin will be summarized descriptively by treatment for each assessment timepoints.

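### MF-7 items are summarised only as percent change, which is undefined from a baseline of 0, so new symptoms in those patients drop out of the item tables

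*SAP*

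**What the plan says.** SAP 2.11, under the MF-7 heading, gives the summary in one sentence: "Percent change from Baseline in MF-7 total symptom score and 7 individual symptoms at each visit will be summarized with descriptive statistics". The rest of the visible MF-7 text deals with missing items and missing totals. It names no observed post-baseline score, no absolute change and no handling of a zero baseline. SAP 2.5 refers to the PRO section for MF-7.

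Protocol 7.2.5 scores each of the seven items from 0, meaning absent, to 10. Inclusion criterion 5 (Protocol 5.2) requires a total of at most 15, "with each individual symptom score of ≤ 3". Neither limit has a lower bound.

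For efficacy and other non-safety evaluations, SAP 2.1.8 states that "the last available assessment before or on the day of randomization is taken as the" baseline. Since "the patient must have baseline assessments performed on Day 1 prior to randomization and treatment initiation" (Protocol 7.1.2.3), this will normally be the Day 1 value.

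The spleen endpoints are treated differently. SAP 2.5 asks for the observed volume and length together with "absolute change and percentage change in spleen volume by MRI/CT and palpable spleen length below costal margin".

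**The concern.** A score of 0 is the natural starting point for a symptom the patient does not have. With percent change as the only statistic, such a patient has no value for that item at any later visit and is silently removed from its table. The loss is one-sided. A new symptom going from 0 to 7 is omitted, while a change from 1 to 0 stays in as −100%. The number analysed can also differ between items and between arms without being reported.

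This bears on what the trial set out to learn, because Protocol 10.4.1 describes the aim as delaying the emergence of MF symptoms. The early-termination SAP derives no PFS (2.5) and performs no secondary efficacy analysis (2.7), so time to symptomatic progression is gone. The optional repeated-measures model of Protocol 10.5.6 does not appear in the visible SAP. The percent-change table is what remains of MF-7 after baseline.

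A second weakness affects patients who stay in: with baselines of 1 or 2, percent change swings widely for small changes in score.

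**Working it through.** The plan states no figure on this point, so there is none to reproduce. The check is whether the statistic exists for every eligible patient and, if not, what is lost.

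**1. Definition.** Percent change = 100 × (y − b) / b, with b the baseline and y the later score. At b = 0 it has no value.

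**2. Can b be 0?** Yes: the scale starts at 0 and eligibility sets no minimum. The item cap is a screening criterion, and Protocol 7.1.2 makes a patient a screen failure if the medical condition changes significantly during screening "so that the inclusion/exclusion criteria are no longer met". Low values are thus to be expected whether baseline is the screening or the Day 1 score. The smallest total with no item at 0 is 7 × 1 = 7. Every patient with a baseline total of 6 or less therefore has at least one item at 0.

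**3. How many patients leave an item table?** The share z of zero baselines on an item is not documented, so a range is used, with an assumed 10 patients per arm.
- Mean number kept = 10 × (1 − z).
- Chance of losing at least one = 1 − (1 − z)^10.

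**4. What does the selection do to the average?** Assume that every patient has a 30% chance of +2 points, and that patients above 0 also have a 30% chance of −1.
- All patients: z × (0.3 × 2) + (1 − z) × (0.3 × 2 − 0.3 × 1) = 0.30 + 0.30z.
- Patients kept: 0.3 × 2 − 0.3 × 1 = 0.30.

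Both are absolute changes, so the comparison isolates who is dropped from the effect of the percent scale. The share of worsening patients left out equals z.

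| z | Mean kept of 10 | Chance of losing ≥ 1 | Mean change, all | Mean change, kept |
|---|---|---|---|---|
| 10% | 9 | 65% | +0.33 | +0.30 |
| 30% | 7 | 97% | +0.39 | +0.30 |
| 50% | 5 | 99.9% | +0.45 | +0.30 |
| 70% | 3 | > 99.9% | +0.51 | +0.30 |

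**5. Extreme case (constructed), one item.** Baseline 0, 0, 0, 1, 1, 2, 2, 2, 3, 3; follow-up 7, 7, 7, 0, 0, 2, 2, 2, 3, 3.
- Absolute change: (3 × 7 − 2 × 1) / 10 = +1.9 points, n = 10.
- Percent change: (2 × (−100) + 5 × 0) / 7 = −28.6%, n = 7, maximum 0%.

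The two summaries point in opposite directions.

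**6. Opposite case, same baselines, all ten worsen by 1.** Absolute change is +1.0, n = 10. Percent change is (2 × 100 + 3 × 50 + 2 × 33.3) / 7 = +59.5%, n = 7. The direction survives, although three patients are still missing.

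**7. Scale effect on the total.** The same 7-point rise reads 7/1 = +700%, 7/5 = +140% or 7/15 = +47%, according to the baseline total.

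**The case against.** Several points on the other side are fair.

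- **The measure comes from the protocol.** Protocol 10.5.6 already names percent change for MF-7. This stands: the SAP inherits the gap, and the remedy improves a protocol-specified summary.
- **Exclusion depends only on a pre-randomization value.** With 1:1 randomization the excluded patients are balanced between arms in expectation, and those kept form a legitimate baseline-defined subgroup. This also stands. The defect is that each item table describes a narrower population, with chance differences in number between arms. It is not a built-in bias between arms.
- **New symptoms may show elsewhere.** SAP 2.1.10 says "Data from all assessments (scheduled and unscheduled), including multiple assessments, will be listed". Sites review questionnaires for possible adverse events (Protocol 7.2.5), and treatment-emergent events are tabulated (SAP 2.8.1). This helps in part, but confirmed progression is not reported as an adverse event (Protocol 8.1.1), and a listing does not repair a table whose denominator has shrunk.
- **The general wording in SAP 2.5 might allow absolute change.** It promises descriptive statistics for the endpoints of interest but refers to the PRO section for MF-7, where only percent change is named.
- **Hidden text could contain a rule.** Parts of the PRO section are redacted or not shown, so the finding is confined to what is visible.
- **The illustrations are invented.** Arm size, z and the change probabilities are assumptions, and the extreme case was chosen to be extreme. They show what can happen, not what did.

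**Conclusion.** The concern holds. As the visible SAP is written, a patient with an item baseline of 0 has no percent change for that item and by default disappears from its table, taking any new symptom along. This follows from the scale and the definition and needs no assumption about frequency. How often it happens depends on the undocumented share of zero baselines; at 10% to 70%, an assumed arm of 10 keeps 9 down to 3 patients on average.

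The effect is confined to the item tables unless all seven baseline items are 0, when the total is undefined too. Its importance is moderate. There is no formal PRO test, SAP 1.2 calls the numbers randomized and the study duration minimal, and no inferential conclusion rests on these tables. The change should still be made, because in so small a study each omitted patient weighs heavily and the SAP already uses the better summary for the spleen. There a non-palpable spleen also has length 0, but absolute change keeps the patient in.

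**What to change.** In SAP 2.11, for the MF-7 total and each of the 7 items:

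1. Summarise the observed score and the absolute change from baseline, by visit and arm.
2. Keep percent change, computed only where the baseline is above 0.
3. Report, by arm, the number of patients excluded from each percent-change summary because of a zero baseline.

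This costs two or three sentences and a small programming change, with no new data.

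A separate, minor point in the same section concerns EQ-5D. Protocol 10.5.6 and SAP Table 1-1 call for change from baseline, but the EQ-5D text of SAP 2.11 gives only dimension levels and VAS values by visit, and SAP section 4 records no departure. Either add change from baseline for the VAS and the dimensions (for example, a shift from the baseline level), or record the departure in section 4.
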